12.1 Toxicity Scale

The Investigator will grade the severity of each AE according to the “Common Terminology Criteria for Adverse Events (CTCAE)” (v 5.0) which can be found at

https://ctep.cancer.gov/protocolDevelopment/electronic_applications/ctc.htm

12.2 Causality

Causality (likelihood that the event is caused by the study agent) will be assessed considering the factors listed under the following categories:

Definitely Related

- reasonable temporal relationship
- follows a known response pattern
- clear evidence to suggest a causal relationship
- there is no alternative etiology

Probably Related

- reasonable temporal relationship
- follows a suspected response pattern (based on similar agents)
- no evidence of a more likely alternative etiology

Possibly Related

- reasonable temporal relationship
- little evidence for a more likely alternative etiology

Unlikely Related

- does not have a reasonable temporal relationship
OR
- good evidence for a more likely alternative etiology

Not Related

- does not have a temporal relationship
OR
- definitely due to an alternative etiology

Note: Other factors should also be considered for each causality category when appropriate. Causality assessment is based on available information at the time of the assessment of the AE. The investigator may revise the causality assessment as additional information becomes available.

12.3 Recording/Documentation

At each contact with the participant, information regarding AEs will be elicited by appropriate questioning and examinations. All events, both expected/unexpected and related/unrelated will be recorded on a source document. Source documents may include, but not limited to, progress notes, laboratory reports, consult notes, and phone call summaries. Source documents will be reviewed in a timely manner by the research team. All reportable AEs that are identified will be recorded in CRIMSON. The start date, the stop date, the severity of each reportable event, and the principal investigator's judgment of the AE's relationship and expectedness to the study agent will also be recorded in CRIMSON.

12.4 Expected Events

Some signs or symptoms are induced by or associated with methylprednisolone sodium succinate, and any combination of these is expected to occur. These events will not be reported unless they reach a grade of 3 or higher (as defined in the CTCAE, v 5.0), are deemed a risk to the participant's rights or wellbeing, or are deemed appropriate to report under specific circumstances by the principal investigator. Examples include:

- Hyperglycemia
- Leukocytosis
- Neutrophilia
- Monocytopenia
- Eosinopenia
- Flushing

- Change in appetite
- Bitter taste in mouth
- Metallic taste in mouth
- Anxiety
- Changes in mood
- Insomnia
- Lymphopenia (only reported if grade 4 or above)

12.5 Type and Duration of the Follow-up of Participants after Adverse Events

AEs related to research procedures will be followed through resolution or until the investigator determines the event has stabilized and no additional follow-up is required. AEs related to the methylprednisolone infusion that have not resolved by the end of study participation will be followed until they have returned to baseline values. If it is not possible to obtain a final outcome for an AE (eg, the participant is lost to follow-up), then the reason a final outcome could not be obtained will be recorded by the investigator in CRIMSON.

12.6 Halting Rules for the Protocol

Halting the study requires immediate discontinuation of study agent administered for all participants and suspension of enrollment until a decision is made whether or not to continue enrollment and study agent administration.

The halting rules are:

- 2 or more participants experience the same or similar SAEs that are possibly, probably, or definitely related to the study agent;
OR
- any safety issue that the principal investigator determines should halt the study.

The principal investigator will determine if the study should be halted. The data and safety monitoring board (DSMB) may also recommend a halt.

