5.1 Disposition, Dispensation, and Accountability

The study agent, methylprednisolone sodium succinate, will be distributed and accounted for by the NIH pharmacy according to standard pharmacy procedures.

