12.6.1 Reporting a Study Halt

If a halting rule is met, then a description of the AE(s) or safety issue must be reported by the principal investigator within 1 business day to the IRB. The principal investigator will also notify the DSMB.

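### Relatedness and the counted halting rule refer only to the infused drug, so a serious event that begins during the protocol taper gets no taper-relatedness grade and cannot count toward a halt

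*Combined protocol and SAP*

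**What the plan says.** Section 12.2 sets the object of the causality scale: "Causality (likelihood that the event is caused by the study agent) will be assessed". Section 12.3 carries the same object into the database, where the investigator's judgement of "relationship and expectedness to the study agent will also be recorded in CRIMSON". Section 5.1 says what the agent is: "The study agent, methylprednisolone sodium succinate, will be distributed and accounted for by the NIH pharmacy". The oral glucocorticoid being withdrawn is not part of it.

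Section 12.6 gives two halting rules. The counted one is met when "2 or more participants experience the same or similar SAEs that are possibly, probably, or definitely related to the study agent". The other is "any safety issue that the principal investigator determines should halt the study". The DSMB may also recommend a halt, and under section 12.6.1 a met rule "must be reported by the principal investigator within 1 business day to the IRB". The effect of a halt is defined in terms of the infused drug and recruitment: "Halting the study requires immediate discontinuation of study agent administered for all participants and suspension of enrollment".

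The taper is a second intervention. Inclusion criterion 8A (section 4.2) makes agreement to it a condition of entry for non-flaring participants on glucocorticoid at up to 10 mg/day, section 6.2 and its Table 1 give the weekly schedule, and section 8.1 lists destabilisation of lupus and flare as its risk. Section 12.5 recognises harms from sources other than the infusion: "AEs related to research procedures will be followed through resolution or until the investigator determines the event has stabilized".

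**The concern.** The protocol imposes two interventions that can cause serious harm, and its formal relatedness tools look at only one of them. The taper comes first, in people whose disease is controlled on treatment, within a study that section 8.2 says is not designed to benefit them. If several participants had similar serious flares while tapering, the database would show those events as unlikely or not related to the agent. No recorded field would show that anyone had judged them related to the taper, and no pre-stated number would prompt a pause.

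Section 12.5 makes the gap more visible. It sets follow-up for adverse events related to research procedures, but sections 12.2 and 12.3 provide neither a scale nor a field for making that judgement.

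What is at stake is participant safety oversight and the clarity of the safety record. Nothing here bears on the differential-expression analysis.

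**Working it through.** The plan gives no figure to reproduce: the count of two is stated without an assumed event rate. The check is to set the sections side by side and then work out how long the uncovered period lasts.

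**Can a pre-infusion SAE meet the counted rule?**

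1. To count, the SAE must be graded possibly, probably or definitely related to the study agent (12.6).
2. Each of those three grades in section 12.2 lists a reasonable temporal relationship among its factors.
3. The study agent is the methylprednisolone infusion (5.1), given once at the infusion visit (6.3).
4. For participants who taper off completely, infusion follows about 10 calendar days after the last oral dose (6.2).
5. An event that begins before the infusion has no reasonable temporal relationship to it. The remaining grades are unlikely related and not related, and neither counts.

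The scale does return a grade, but it answers a question about the infusion. No scale or field asks about the taper.

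**How long is the period?**

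Inputs: Table 1 in section 6.2 lowers the dose by 2.5 mg each week down to 5 mg/day and then by 1 mg each week. The steroid-free interval is about 10 days. Counting starts at the first dose reduction and assumes the taper is completed.

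Days = 7 × (number of reduced, non-zero dose levels) + 10

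| Starting dose (mg/day) | Reduced levels (mg/day) | Days |
|---|---|---|
| 10 | 7.5, 5, 4, 3, 2, 1 | 6 × 7 + 10 = 52 |
| 7.5 | 5, 4, 3, 2, 1 | 5 × 7 + 10 = 45 |
| 5 | 4, 3, 2, 1 | 4 × 7 + 10 = 38 |
| 2 | 1 | 1 × 7 + 10 = 17 |
| 1 | none | 0 × 7 + 10 = 10 |

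The starting point is a convention. Counting a further week at the full starting dose adds 7 days, giving 59 from 10 mg/day. A taper that ends early in flare is shorter, with infusion scheduled within 7 days of the flare being documented.

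**What cannot be computed.** The documents give neither the number of participants who will taper nor their SAE risk, so no probability of two such events is offered.

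**The case against.** The strongest reply is that taper events are already well guarded, and much of it stands.

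- Entry to the taper is limited to stable doses of at most 10 mg/day without escalation of other immunosuppression, and section 6.2 describes these patients as good candidates for tapering in ordinary practice.
- The lupus unit's clinicians manage the taper, which stops at clinical evidence of flare. A participant whose flare needs intervention is withdrawn and treated (6.2, 12.8).
- The investigator can halt for any safety issue, with the same one-business-day report. SAEs go to the DSMB (14.2), and the IRB or NIAID can stop the study (12.7). Even when the count is met, the investigator decides whether to halt.
- Flare is background disease, there is no untapered control, and flare during the taper is one of the things section 6.2 sets out to study. A count could therefore fire on events the taper did not cause.

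These points rule out several stronger readings. A reader might infer that the study cannot be halted for taper harm, or that such events go unseen; the routes above show otherwise. A reader might infer that an SAE caused by the taper can never count, but one that starts after infusion could still be graded possibly related to the agent. Nor do the documents suggest that a participant in mid-taper would be left without care on a halt. They only lack text specific to that case.

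What the reply does not supply is a taper-relatedness grade or a pre-set count. Withdrawal protects one person at a time and does not add events up across participants. The plan adopted a count for the infusion even though the same discretionary routes were available.

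**Conclusion.** The point holds in a narrow form. Under sections 12.2, 12.3 and the counted line of 12.6, an SAE that begins after the taper starts and before infusion has no grade for relatedness to the taper and cannot count toward the two-participant trigger. For completed tapers this covers about 10 to 52 days, depending on starting dose. Other routes to a halt exist, so this is a modest safety improvement.

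It is tempting to express the gap as a share of each participant's time on study. That is not supported. The share changes with starting dose and with where follow-up is taken to end, and pre-infusion time falls outside a rule about the infused drug whether or not anyone is tapering.

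The conclusion rests on the weekly steps in Table 1, on an interval of about 10 days, and on reading a reasonable temporal relationship as requiring that the infusion came first. NIH HRPP Policy 801, to which the protocol refers for event definitions and reporting, is not among the documents and could not be checked.

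**What to change.** 1. In sections 12.2 and 12.3, grade and record the relationship to the protocol glucocorticoid taper as well as to the study agent, on the same five-level scale. This also supplies the judgement that section 12.5 relies on.
2. In section 12.6, extend the counted rule to SAEs graded at least possibly related to either the study agent or the protocol taper. State that a taper trigger pauses new tapers and prompts DSMB review of those under way, while participants who need no taper continue.

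The cost is a protocol amendment and one extra causality field in CRIMSON. The downside is that two serious background flares could pause tapering until the DSMB has reviewed them. Limiting the pause to tapering keeps that cost small.

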12.6.1 Reporting a Study Halt

If a halting rule is met, then a description of the AE(s) or safety issue must be reported by the principal investigator within 1 business day to the IRB. The principal investigator will also notify the DSMB.

12.6.2 Resumption of a Halted Study

The principal investigator, in collaboration with the DSMB, will determine if it is safe to resume the study. The principal investigator will notify the IRB of the decision on resumption of the study.

12.7 Study Discontinuation

The IRB, the NIAID, and other oversight bodies as applicable, as part of their duties to ensure that research participants are protected, may discontinue the study at any time. Subsequent review of serious, unexpected, and related AEs by the IRB may also result in suspension of enrollment and further administration of study agent.

12.8 Premature Withdrawal of a Participant

An individual participant will be withdrawn for any of the following:

- An individual participant's decision. (The investigator should attempt to determine the reason for the participant's decision.)
- Non-compliance with study procedures to the extent that it is potentially harmful to the participant or to the integrity of the study data.
- A participant becomes pregnant between screening and the infusion visit.
- A participant experiences a disease flare during tapering of current glucocorticoid therapy that requires intervention before the infusion visit.
- A participant experiences an anaphylactoid reaction, anaphylaxis, or angioedema requiring medical therapy during the glucocorticoid infusion.
- The investigator determines that continued participation in the study would not be in the best interest of the participant.
- A participant who has a flare at screening visit and not scheduled for infusion within 7 days or needs to receive glucocorticoids before the scheduled infusion visit.

12.9 Replacement of Withdrawn Participants or Participants Who Discontinue Study Treatment

Participants who withdraw or are withdrawn from the study prior to the infusion visit will be replaced.

13 Reporting Procedures

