3.1 Description of the Study Design

Potential participants will present to the NIH CC for a screening visit. Objective documentation of the diagnosis of SLE, the specific clinical manifestations, and the level of disease activity will be established. A baseline whole blood sample will be obtained at screening. Each enrolled participant will be randomly assigned to 1 of 2 methylprednisolone dose groups: 1 mg/kg or 250 mg.

All enrolled participants will return for a day-long study visit (“infusion visit”) within 75 days of the screening visit. Following collection of a pre-infusion whole blood sample, participants will receive a single IV dose of methylprednisolone (based on the dose group assignment), infused over 30 minutes. Whole blood samples will then be obtained serially, 2 and 4 hours after the start of infusion.

Participants will be discharged after collection of the 4-hour blood sample, measurement of vital signs, and documentation of any adverse events (AEs). Two follow-up phone calls will be made to document any AEs related to the methylprednisolone. If any AEs that may require treatment are documented on the follow-up phone calls, then participants will be asked to return to the NIH CC’s outpatient clinic for evaluation by the principal investigator.

We propose an adaptive study design, in which we will recruit an initial cohort of 20 participants into each of the 2 dosing groups. After processing the samples from these participants, we will perform differential expression analysis to determine if recruitment of additional participants (up to the accrual ceiling of 100) would affect the biological interpretation of the data. If additional data would be unlikely to change the study outcome, then no further recruitment will be pursued.

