5.4 Randomization

Study participants will be randomized evenly to 2 dose groups. The purpose of randomization in this setting is to produce balanced dose groups where participants are comparable between groups in terms of possible confounding factors such as age, sex, or concomitant medication use. To further ensure that participants are similar in terms of SLE severity between the groups, we will adopt stratified randomization according to their disease activity using the Safety of Estrogens in Lupus Erythematosus National Assessment SLE Disease Activity Index (SELENA/SLEDAI) score on the day of enrollment. Participants will be classified into 1 of 3 disease-severity categories: low (SELENA/SLEDAI score = 0-4), intermediate (SELENA/SLEDAI score = 5-8), or high (SELENA/SLEDAI score > 9). Randomization will be carried out within each category. This stratified randomization method ensures the proportion of participants with high disease activity is the same between the dose groups.

The study statistician will design the randomization scheme. The randomization code list will be maintained by the study statistician and the study coordinator.

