The above criteria will apply irrespective of whether the patients are on glucocorticoid therapy at the time of their screening visit, but patients who are experiencing a lupus flare while on glucocorticoid therapy will not be deemed eligible for a glucocorticoid taper. For patients on glucocorticoid therapy who are experiencing a lupus flare at the time of their screening visit, the maximum prednisone or prednisone-equivalent dose will be ≤ 15 mg/day. Patients on higher doses of chronic glucocorticoid therapy who are experiencing a flare are deemed likely to require an infusion earlier than 7 days after evaluation and will thus be excluded.

If a patient who is experiencing a lupus flare on the day of the screening visit is enrolled, but the infusion visit is later delayed beyond 7 days after enrollment or the severity of the flare increases to the point where glucocorticoids must be administered before the infusion visit can be scheduled, glucocorticoid treatment will be administered as clinically indicated and the patient will be withdrawn from the study.

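### As naturally read, the dose is assigned well before infusion with no concealment described, so dose-dependent loss before dosing could bias the secondary dose comparison, and the stratifying score may be out of date by then

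*Combined protocol and SAP*

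**What the plan says.** - **Assignment.** Section 3.1, in its paragraph on the screening visit: "Each enrolled participant will be randomly assigned to 1 of 2 methylprednisolone dose groups: 1 mg/kg or 250 mg". The next paragraph places the infusion visit "within 75 days of the screening visit".
- **Stratification.** Section 5.4 forms three strata from the SELENA/SLEDAI "score on the day of enrollment". It adds "Randomization will be carried out within each category" and concludes: "This stratified randomization method ensures the proportion of participants with high disease activity is the same between the dose groups".
- **Custody of the list.** Section 5.4: "The randomization code list will be maintained by the study statistician and the study coordinator". No section describes masking, or says when an assignment is made known and to whom.
- **The interval.** Section 6.2 allows a taper after eligibility is confirmed. It ends at zero dose, followed by a wait of about 10 days, or at a flare, followed by infusion within 7 days. Section 6.1.1 gives participants in flare at screening at most 7 days from enrolment. If that slips, or the flare worsens, "glucocorticoid treatment will be administered as clinically indicated and the patient will be withdrawn from the study".
- **Loss before dosing.** The reasons in Section 12.8 include the participant's own choice, the investigator's view of the participant's interest, a taper flare needing intervention first, and a screening flare not infused in time. Section 12.9: "Participants who withdraw or are withdrawn from the study prior to the infusion visit will be replaced". It does not say how a replacement is allocated.
- **Re-scoring.** Section 6.3 repeats the SELENA/SLEDAI on infusion day only when the taper ended in a flare. Section 7 gives the score a 28-day look-back.
- **Analyses.** The primary endpoint (Sections 3.2.1 and 15.3) is change from baseline within each dose. The dose comparison is secondary endpoint 1. Section 15.3 describes it as a contrast of the two groups at the same time point and names no adjustment for stratum or baseline.

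**The concern.** Randomisation protects a comparison from the moment of assignment. Here, on the natural reading, weeks may pass between assignment and dose, and people can leave in that time for reasons that partly call for judgment: whether a flare can wait, or whether continuing is in the participant's interest. If those deciding know the assigned dose, the decision can depend on it. The two groups that reach infusion could then differ in disease activity for reasons other than chance, and the dose comparison in Section 15.3 would carry that difference into the expression contrast. The between-dose gene subset also feeds the decision in Section 15.6 to stop or extend recruitment.

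Separately, the stratum is fixed before a taper that Section 6.2 recognises may raise disease activity. The equality that Section 5.4 claims may therefore no longer describe the people who are dosed.

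**Working it through.** **1. The plan's own power figure.** Section 15.6 gives 90% power at 0.72 SD with 20 per group, by a paired test. Assuming two-sided alpha of 0.05:

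Φ(0.72 × √20 − 1.96) = Φ(3.22 − 1.96) = Φ(1.26) = 89.6%

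This reproduces the figure by normal approximation; the exact two-sided paired t-test gives 86.3%. The calculation concerns change within an arm. It does not rely on balance between arms, so it neither supports nor weakens this point.

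**2. Time from the start of a full taper to infusion.** Inputs from Section 6.2 and Table 1: steps of 2.5 mg/week down to 5 mg/day, then 1 mg/week to zero, then about 10 days. With w weekly steps, the time is 7w + 10 days if the first reduction comes after a week, or 7(w − 1) + 10 if it comes at once.

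| Starting dose | Steps w | 7(w − 1) + 10 | 7w + 10 |
|---|---|---|---|
| 10 mg/day | 7 | 52 days | 59 days |
| 7.5 mg/day | 6 | 45 days | 52 days |
| 5 mg/day | 5 | 38 days | 45 days |

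All fit inside 75 days, and all exceed the 28-day window of the score. On infusion day the enrolment score of these participants describes a period that no longer overlaps the current window. Low starting doses are different: from 2 mg/day the range is 17 to 24 days.

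**3. Whose score is renewed.** Taper ended in flare: repeated on infusion day, but after the stratum was set. Taper completed to zero: no repeat specified. Flare at screening: no repeat, but infusion is due within 7 days of enrolment, so the score is about a week old at most. No taper and no flare: no repeat, with up to 75 days from screening.

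**4. What loss does to the dose comparison.** Everyone covered by Section 12.9 is undosed.

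- If the chance of loss does not depend on assigned dose, the expected difference between arms is 0, with or without replacement.
- If it does depend on dose, the shift can be illustrated. Assume disease activity is normal and only the most active fraction f is lost, in one arm only, with replacements subject to the same loss. That arm's mean falls by φ(c)/(1 − f) SD, where c is the (1 − f) quantile.

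| Assumed f | Shift in that arm's mean activity |
|---|---|
| 5% | 0.11 SD |
| 10% | 0.19 SD |
| 20% | 0.35 SD |
| 30% | 0.50 SD |

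These are extreme cases: total selection on activity, and in one arm. The documents supply neither a loss rate nor evidence that loss would differ by arm.

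**The case against.** **The moment of randomisation is never written down.** True. Section 3.1 says who is assigned and Section 5.4 says which day's score is used; neither says when the assignment is made or released. Assignment at or near enrolment is the natural reading, not a stated fact.

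**Nothing shows that the clinicians know the dose.** Also true. The statistician and coordinator hold the list, while Lupus Clinical Trials Unit staff manage the taper. But no text keeps the assignment from those staff or from the participant, so dose-dependent loss is left open rather than shown.

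Three stronger readings are tempting and are not supported:

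- *Replacement by itself undoes the randomisation.* A reader might infer this because the people infused are not everyone who was randomised. Loss unrelated to arm leaves the comparison fair in expectation. Nor does Section 12.9 say that a replacement enters the same arm.
- *High-activity participants are the likeliest to be lost.* Section 6.2 describes taper participants as in clinical remission at entry, so taper losses may come mainly from people with low activity at enrolment. Section 6.1.1 admits only those screening flares that do not need glucocorticoids before infusion.
- *The primary endpoint is compromised.* It is a before/after change within participants. Losses may affect whom the results represent, but the contrast does not rest on balance between arms.

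**An out-of-date stratum does not invalidate randomisation.** This stands. If loss and the course of the taper do not depend on dose, activity at infusion is still balanced in expectation. What weakens is control of chance imbalance at 20 per arm, and with it the claim that equality is ensured. The plan does re-score participants whose taper ended in flare, but that score does not enter the stratification.

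**Conclusion.** The point holds as a design weakness affecting the secondary dose comparison. On the natural reading of Sections 3.1 and 5.4, assignment precedes an interval of up to 75 days (at most 7 days from enrolment for participants in flare at screening) in which withdrawal can turn on judgment and is followed by replacement. With no concealment described, the plan does not exclude loss that depends on the assigned dose. The claim of equal proportions with high activity applies at enrolment and not necessarily among those dosed, because a full taper from 5 to 10 mg/day plus the wait takes about 38 to 59 days against a 28-day score window.

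The size of any imbalance is unknown. The shifts of 0.11 to 0.50 SD above rest on assumed one-arm loss of 5% to 30% and show what is possible, not what is expected. The conclusion assumes that assignment is made at or near enrolment and can be known before dosing. If the sponsor already withholds it until infusion, the bias concern falls away and only the age of the stratifying score remains.

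**What to change.** **Sections 3.1 and 5.4.** State that the allocation is generated or released at the infusion visit, after the pre-infusion checks are complete and just before the dose is prepared. Stratify on the most recent available SELENA/SLEDAI: the infusion-day score where Section 6.3 already requires one, built from the components available before dosing, and otherwise the screening score. Reword the claim of ensured balance to match.

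**Section 12.9.** State that pre-infusion withdrawals occur before randomisation, so that enrolment continues until the target number is infused and no replacement within an arm is needed. Report their number and reasons.

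**Section 15.3.** Include the stratum and the pre-infusion expression value in the dose comparison. This matters most for participants not re-scored, whose stratum remains the screening score.

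If assignment must stay early, the lesser remedy is to conceal it until dosing, say how replacements are allocated, report pre-infusion losses by arm and stratum, and make the same change to Section 15.3.

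**Cost.** Mostly protocol wording, plus same-day allocation and dose preparation by the pharmacy. Recruitment is not increased. Reaching 40 infused takes 40/(1 − loss) enrolled under either order, rounded up: 43, 45, 50 or 58 at an assumed loss of 5%, 10%, 20% or 30%. The change only moves those losses ahead of randomisation. Scoring everyone at infusion would also renew the remaining strata, but it adds assessments and is not needed for the main fix.
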